4. STUDY DESIGN

4.1 Background

Patients with Obstructive Sleep Apnoea (OSA) experience interrupted and reduced sleep which can have a significant impact on quality of life and increases the risk of developing certain conditions. Mild OSA, unlike moderate and severe OSA, has not been extensively studied. Although there is a reasonable pool of evidence that suggests that even minor sleep related breathing disturbances are associated with negative consequences, there is no consensus on when treatment should be initiated or the best treatment for mild OSA patients. Two previous clinical trials have suggested that treating mild OSA with Continuous Positive Airway Pressure (CPAP) improved symptoms, quality of life and reduced health risks in these patients. However, despite this evidence, treatment with CPAP for mild OSA is not consistently offered.

CPAP is a treatment that uses mild air pressure to keep the airways open during sleep. The machine (ResMed AirSense S10) consists of a mask that fits over the nose, a tube that connects the mask to the machine motor and the motor which blows air through the tube to the mask.

Mild OSA is defined as Apnoea Hypopnoea Index (AHI) of 5 up to 15 events/hour. Mild OSA patients will be identified using **American Academy of Sleep Medicine (AASM)** 2007 and 2012 guidelines as described below.

In 2012, the American Academy of Sleep Medicine (AASM) changed the criteria needed to score a hypopnoea during a sleep study. Previous 2007 criteria had required a hypopnoea to include a decrease in oronasal airflow by $\geq 30\%$ from baseline, an event of at least 10 seconds, and $\geq 4\%$ SpO₂ desaturation. These criteria had been widely accepted by healthcare providers to form the basis of

diagnosis, access to treatment, and reimbursement for patient equipment. In 2012, a change was made to these criteria which permitted hypopnoeas to be scored with an arousal only, or an oxygen desaturation of $\geq 3\%$. The newer criteria of OSA defined by the AASM in 2012 are broader and increase the percentage of patients who may be diagnosed with OSA, potentially by up to 40%.

Guideline	Recommended Hypopnea Definition per Guidelines:
AASM 2007	
 • A decrease in oronasal airflow by $\geq 30\%$ from baseline AND • The event is ≥ 10 sec long AND • Associated with $\geq 4\%$ SpO_2 desaturation

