4.2 Enrolment Target and Inclusion/Exclusion Criteria

The MERGE study is a prospective multicentre randomised parallel trial with 3 months of active treatment versus a control arm. Randomisation with minimisation will be performed with a 1:1 treatment group allocation.

Date of start of recruitment:	26 October 2016
Date of expected end of recruitment:	31 December 2018
Date expected end follow-up:	31 March 2019
Target number of subjects:	224 (112 per arm)
Participating Centres:	11

A patient will be eligible for inclusion in the study if all the following inclusion criteria apply:

- AHI 5-15 events/hr as per AASM 2007 scoring criteria or AHI ≥ 5 per AASM 2012 if AHI 0-4.9 per AASM 2007
- Aged ≥ 18 and ≤ 80 years
- Ability and willingness to provide written informed consent
- Ability to tolerate a CPAP one hour long run-in test

A patient will not be eligible for the study if any of the following exclusion criteria apply:

- The presence of unstable cardiac disease at trial screening
- Inability to give fully informed consent
- Use of supplemental oxygen
- Secondary sleep pathology e.g. Periodic Limb Movement Syndrome, Narcolepsy, Circadian Disorder, Obesity Hypoventilation Syndrome
- Epworth Sleepiness Scale (ESS) ≥ 15 , or concerns about sleepy driving from physician/ sleep lab staff
- Body Mass Index (BMI) $\geq 40 \text{ kg/m}^2$
- Previous CPAP usage

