4.5 Study Objectives

This study aims to assess the changes in quality of life from baseline to 3 months in mild OSA patients (based on AASM 2012 guidelines) comparing the Treatment and Control groups.

The objectives of the study are as follows:

Primary Objective:

- Compare the change in quality of life (SF-36 energy and vitality subscale score) from baseline (pre-treatment) to 3 months between Treatment and Control groups in patients with mild OSA **per AASM 2012** guidelines.

Secondary Objectives:

- Compare changes in quality of life scores (SF-36, ESS, FSS, FOSQ, HADS, ISI and EQ-5D) from baseline (pre-treatment) to 3 months between Treatment and Control groups in patients with mild OSA **per AASM 2012** guidelines.
- Compare changes in quality of life scores (SF-36, ESS, FSS, FOSQ, HADS, ISI and EQ-5D) from

baseline (pre-treatment) to 3 months between Treatment and Control groups in patients with mild OSA **per AASM 2007 guidelines**.

Exploratory Analyses:

- Compare changes in quality of life scores (SF-36, ESS, FSS, FOSQ, HADS, ISI and EQ-5D) from baseline (pre-treatment) to 3 months between Treatment and Control groups in patients with moderate to severe OSA **per AASM 2012 guidelines**.
- Compare changes in quality of life scores from baseline to 3 months between Treatment and Control groups for patients with no OSA ($AHI < 5$) **per AASM 2007 guidelines** but who enter the study ($AHI \geq 5$) **per AASM 2012 guidelines**.
- Assess the impact of adherence to CPAP in the Treatment group, comparing changes in quality of life scores from baseline to 3 months for patients adherent and not adherent to CPAP over the course of study.
- Explore variation in the treatment effect on the change in quality of life scores (SF-36 energy and vitality subscale score, ESS, and FSS) from Baseline to 3 months over the continuous baseline measures of age, BMI, and AHI (as a continuous measure of OSA severity), separately for AASM 2007 and AASM 2012 guidelines.
- Assess the number of patient telephone contacts, clinic visits and other types of intervention required to support CPAP adherence, including the impact of missed contacts, in the Treatment group, comparing results between patients adherent and not adherent to CPAP.
- Compare baseline symptoms and changes in quality of life scores from baseline to 3 months between Treatment and Control groups by gender.
- Compare change from baseline to 3 months in weight and BMI between Treatment and Control groups.

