5. STATISTICAL METHODS

5.1 Study Populations and Analysis Groups

There are two main study populations in this trial, one group fulfilling the mild OSA AASM 2012 guidelines and the second fulfilling the mild OSA AASM 2007 guidelines. Some trial patients will fulfil both criteria and will therefore be eligible for analysis under both AASM 2007 and AASM 2012. A third study population will consist of patients who fall into the category of Moderate to Severe OSA based on the AASM 2012 guidelines. Patients in this third population will either have tested as No OSA (AHI < 5 e/hr) or Mild OSA based on AASM 2007 guidelines.

The primary endpoint analysis will only be conducted on mild OSA patients per AASM 2012 guidelines. Each secondary endpoint analysis will be carried out on mild OSA patients based on AASM 2012 and AASM 2007 guidelines. Additionally, secondary analyses will be generated descriptively for the subgroup of patients with Moderate to Severe OSA per AASM 2012 guidelines. Therefore, all patients randomised into the trial will be analysed in one or more secondary analyses, with a subset of these patients fulfilling the AASM 2012 guidelines and qualifying for the primary analysis.

The intention to treat (ITT) analysis population will include all randomised patients. The ITT population will be further subdivided as follows:

ITT-1 population includes patients in the ITT with mild OSA per AASM 2012 guidelines.

ITT-2 population includes patients in the ITT with mild OSA per AASM 2007 guidelines.

ITT-3 population includes patients in the ITT with moderate to severe OSA per AASM 2012 guidelines.

The primary endpoint analysis, pool-ability analysis (see Section 5.3) and comparability of baseline characteristics will be generated for the ITT-1 population.

The completed cases (CC) analysis population will be a subset of the ITT population that includes patients who complete the 3-month study visit. [It is possible for there to be missing values for one or more outcome measures in the CC group, if a patient who completes the visits does not complete the questionnaires completely.] The CC population will be further subdivided as follows:

CC-1 population includes patients in the CC with mild OSA per AASM 2012 guidelines.

CC-2 population includes patients in the CC with mild OSA per AASM 2007 guidelines.

CC-3 population includes patients in the CC with moderate to severe OSA per AASM 2012 guidelines.

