The primary endpoint measure (mean change in Energy and Vitality subscale) will be examined over the spectrum of baseline AHI scoring as a continuous variable to investigate trends in the relationship between the two variables. Scatter plots of baseline AHI versus the primary endpoint will be generated for each treatment group. Statistical modelling may be performed to describe any observed variation in treatment effect related to baseline AHI. The primary endpoint will also be examined for any relationship between treatment effect and age or baseline BMI, using the methods described for AHI. These summaries will be produced for the ITT-1 population.

Mean change in ESS and FSS will also be assessed for variation in treatment effect related to baseline AHI, age, or BMI, using the methods described for the primary endpoint.

The primary endpoint measure will also be compared over the spectrum of baseline ODI and RERA scoring in a similar fashion as above. Separate scatter plots will be generated for the Treatment group, distinguishing patients adherent and non-adherent to CPAP.

Baseline and demographic characteristics, AHI, and quality of life scores will be summarized descriptively by gender for the ITT-1 population. Changes in quality of life scores from baseline to 3 months will be summarized descriptively by treatment group and gender, and the effect of gender will be explored by including gender as a fixed effect in the analysis model described in Section 5.7.

Change from baseline to 3 months in weight and BMI will be summarized descriptively by treatment group for the ITT-1 population.

The reason for patient referral will be analysed, comparing the primary endpoint measure by reason for referral separately for each treatment group using descriptive statistics.

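### SAP 5.10 limits the continuous-AHI effect-variation analysis to ITT-1, which omits the AASM 2007 analysis promised in SAP 4.5 and truncates AHI on the AASM 2012 scale

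*SAP*

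**What the plan says.** The exploratory objectives in SAP 4.5 include variation in treatment effect on SF-36 energy and vitality, ESS and FSS over continuous age, BMI and "AHI (as a continuous measure of OSA severity), separately for AASM 2007 and AASM 2012 guidelines".

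SAP 5.10 implements this. The primary endpoint "will be examined over the spectrum of baseline AHI scoring as a continuous variable to investigate trends in the relationship between the two variables", by scatter plots per arm with optional modelling. Age and BMI are handled the same way, and the paragraph closes with "These summaries will be produced for the ITT-1 population". ESS and FSS follow by reference to the same methods.

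The populations are defined in SAP 5.1. For the one used here, "ITT-1 population includes patients in the ITT with mild OSA per AASM 2012 guidelines". ITT-2 is the corresponding mild group under the 2007 scoring, and ITT-3 takes the randomised patients whose 2012 AHI lies above the mild range.

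SAP 4.1 fixes the mild range: "Mild OSA is defined as Apnoea Hypopnoea Index (AHI) of 5 up to 15 events/hour". Eligibility in SAP 4.2 is wider: "AHI 5-15 events/hr as per AASM 2007 scoring criteria or AHI ≥ 5 per AASM 2012 if AHI 0-4.9 per AASM 2007". AHI is therefore capped at 15 on the AASM 2007 scale only.

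**The concern.** There are two separate problems.

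The first is a mismatch between objective and method. The objective covers both scorings. The implementing paragraph names one population, defined by AASM 2012, and does not say which AHI is plotted. An analyst who follows SAP 5.10 literally will not produce the AASM 2007 analysis.

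The second is range restriction. ITT-1 is selected on AASM 2012 AHI, the variable whose effect modification is being studied. Randomised patients above 15 sit at one end of the scale and have the most leverage on a slope, yet they are left out of the one analysis meant to treat severity as a continuum. A flat ITT-1 plot would be weak evidence that benefit does not depend on severity, and a reader could easily take it as more than that.

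**Working it through.** **Reading the sections together.** SAP 5.10 does not mention ITT-2 or an AASM 2007 AHI for this analysis. It is hard to read ITT-1 as shorthand for both, because the SAP names both populations where it means both: baseline sleep-test parameters (5.6), secondary endpoints (5.8) and CPAP usage summaries (5.10). The table list in SAP 7 gives no population for these displays. The amendment in SAP 8 does not touch them. Protocol 5.3 has every home sleep test rescored by AASM 2012, so both AHI values should exist for all randomised patients.

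**Planned figure.** SAP 4.6 gives a difference of 6.6 and SDs of 17.0 and 18.1, with two-sided 5% and 80% power. Pooled SD = √((17.0² + 18.1²)/2) = 17.56. n per arm = 2 × (1.96 + 0.84)² × 17.56² / 6.6² = 111.1, so 112 per arm and 224 in total. This reproduces the plan.

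**Patients outside ITT-1.** With about 300 randomised (SAP 4.6):
- If 224 counts randomised patients, 300 − 224 = 76 (25%) lie outside.
- If 224 counts completers at 10% drop-out, 224/0.9 = 249 are in ITT-1 and 51 (17%) lie outside. In completers that is 0.9 × 300 − 224 = 46.

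So 75-83% of patients stay in the analysis. Protocol 11.2.4 expects few patients above 15, so I also take 20, which is my assumption.

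**Information on the slope.** The SE of the treatment-by-AHI slope is about 2 × SD / √Sxx, where Sxx is the sum of squares of AHI. Assume AHI is uniform on 5-15 for 224 patients and uniform from 15 to U for k more. The documents give neither U nor any distribution.

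- ITT-1: Sxx = 224 × 10²/12 = 1,866.7.
- All randomised: add k(U − 15)²/12 and [224k/(224 + k)] × ((15 + U)/2 − 10)².
- Example, k = 20 and U = 20: 41.7 + 18.36 × 7.5² = 41.7 + 1,032.8. The total is 2,941.1, and the ratio is 2,941.1/1,866.7 = 1.58.

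Information ratio, all randomised to ITT-1, with the SE as a fraction of the ITT-1 SE in brackets:

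| Patients above 15 | U = 18 | U = 20 | U = 25 | U = 30 |
|---|---|---|---|---|
| 20 | 1.42 (0.84) | 1.58 (0.80) | 2.07 (0.69) | 2.74 (0.60) |
| 46 | 1.88 (0.73) | 2.20 (0.67) | 3.25 (0.55) | 4.66 (0.46) |
| 76 | 2.31 (0.66) | 2.80 (0.60) | 4.38 (0.48) | 6.51 (0.39) |

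**What ITT-1 alone can show.** On the same assumptions, the slope SE in ITT-1 is 2 × 17.56 / √1,866.7 = 0.81 points per event/hour. For 80% power the slope must be about 2.80 × 0.81 = 2.28, so the treatment effect must change by about 23 points between AHI 5 and 15. The planned overall effect is 6.6.

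**Range kept on the AASM 2012 scale.** ITT-1 keeps 10/(U − 5): 67% at U = 20, 50% at U = 25 and 40% at U = 30.

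**AASM 2007 scale.** The eligible range is 0-15. The 2012 hypopnoea rule is looser, so AASM 2007 AHI should not exceed AASM 2012 AHI, and ITT-1 patients can lie anywhere in 0-15. ITT-1 therefore loses little of this range. ITT-2 would cut it at 5.

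**The case against.** The case for leaving the text alone has real parts.

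- **The objective does not expressly ask for patients above 15.** SAP 4.5 can be read as pairing each scoring with its mild population, in which case ITT-1 satisfies the AASM 2012 half. This stands. The argument for adding those patients rests on the stated aim of covering the spectrum of AHI and on precision, not on a contradiction.
- **Patients above 15 are an unusual group.** They were eligible only because AASM 2007 scored them at or below 15, so a pooled slope mixes severity with discordance between the scorings. This stands as a caveat on interpretation, and showing ITT-1 alongside meets it.
- **These patients have their own summaries.** SAP 5.10 describes them in CC-3, and SAP 8 defers the moderate-OSA analyses to a later report. A separate descriptive table does not address a trend over continuous AHI.
- **SAP 1 leaves room for exploratory work.** That permits a wider analysis but does not lift the restriction written into 5.10.
- **The gain is uncertain and relies on a linear slope.** This is correct. Multiplying the 23 points by the SE fractions for U = 20-30 leaves a detectable change of about 9 to 18 points per 10 events/hour (0.39 × 23 to 0.80 × 23). Even the wider analysis would remain descriptive.

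A reader might infer that the plan throws away most of the AHI range randomised. The documents do not support this. No AASM 2012 maximum is given, more than half of that range is lost only if the maximum exceeds 25, little is lost on the AASM 2007 scale, and about three quarters or more of patients remain. Nor is the AASM 2007 analysis absent from the plan: SAP 4.5 lists it, and what is missing is its implementation.

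**Conclusion.** The concern holds in a limited form. SAP 4.5 and SAP 5.10 do not match: following 5.10 as written leaves the AASM 2007 half of a stated objective undelivered. This needs no assumption. Separately, the AASM 2012 analysis truncates the modifier at 15 although patients above that value are randomised and measured.

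The size of the precision loss cannot be fixed from the documents. The information ratio is about 1.6-2.1 with 20 patients above 15 and a maximum AHI of 20-25, and about 2.2-6.5 with 46-76 such patients and a maximum of 20-30. It is smaller if those patients cluster just above 15. All of these figures assume uniform AHI, a linear slope, and that everyone outside ITT-1 lies above 15.

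The truncation argument does not extend to age and BMI, because ITT-1 is not selected on either. For them only the missing AASM 2007 version counts.

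Severity is low. The analysis is exploratory, its modelling is optional, and neither the primary result nor the sample size depends on it.

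**What to change.** In SAP 5.10:

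1. Run the AHI effect-variation analysis for SF-36 energy and vitality, ESS and FSS on all randomised patients (ITT), once with AASM 2012 AHI and once with AASM 2007 AHI as the continuous covariate.
2. Keep ITT-1 (AASM 2012 AHI) and ITT-2 (AASM 2007 AHI) as subset displays.
3. State beside the results that patients above 15 on AASM 2012 were eligible only because AASM 2007 scored them at or below 15.
4. For age and BMI, keep ITT-1 and add the ITT-2 version that SAP 4.5 promises.
5. Name the population and AHI scale for each display in the SAP 7 table list.

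The cost is a few lines of SAP text and re-running the same code on data sets that already exist. No new data are needed.

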## 5.5 CPAP Arm

### 5.5.1 CPAP Initiation

Participants randomised into the CPAP group will be set up on the Auto-adjusting CPAP device (ResMed AirSense S10; response setting for male patients, and AutoSet for Her mode for female patients). The participants will be shown the device and given further instructions on how to use it. They will have the opportunity to try on multiple masks in order to find a mask which is well fitting, comfortable, and unobtrusive. All participants will be provided with humidification to alleviate any discomfort from dry air.

Participants will then take home the device and instructions for use, and will be asked to use the device nightly. As part of the CPAP education participants will be provided with CPAP information and internet links, such as the CPAP user guide, the ResMed youtube channel, and NHS CPAP websites, in order to assist them adapting to CPAP use. Participants will also be shown how to view their nightly usage and mask leak data on their device. Participants with a smart phone will also be introduced to the MyAir App (ResMed). The MyAir app wirelessly downloads data from the device and provides feedback, coaching and tips to patients to assist them with using therapy (see Section 0.) **The MyAir App will not be mandatory in this study, but it will be highly recommended to patients.** If participants are unable to use the MyAir App, they will be shown where to find the equivalent information (CPAP device screen + ResMed websites). This information will also be discussed with them by the Trial Sleep Therapist.

It will be explained that participants device data will be wirelessly monitored on an ongoing basis using the ResMed AirView System (see Section 0) and that the Trial Sleep Therapist may contact them if their data shows that their treatment is not optimal (e.g. their compliance is low, mask leak is high, or AHI is not well controlled).

At this point the participants CPAP details will be entered into the wireless monitoring system (AirView).

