## 9.2 ResMed AirSense 10 AutoSet CPAP

The ResMed AirSense 10 AutoSet CPAP is a non-invasive PAP device indicated for the treatment of obstructive sleep apnea in patients weighing more than 30 kg. The device is intended for home and hospital use. It provides a pressure range of 4-20 cm H2O as required to maintain an "air splint" for effective treatment of flow limitation.

The ResMed AirSense CPAP comes in two models, a standard model and an AutoSet for Her model. The devices contain unique algorithms, with the standard model designed to overcome OSA in all patients, Response Setting for mild patients who may have difficulty tolerating high pressures, and the AutoSet for Her designed to treat specific female breathing patterns. All modes are commercially available with CE mark. In this trial, male patients will be given the AutoSet using Response Setting and female patients will be given the AutoSet for Her.

The devices come with in-built humidification and heated tubing which heats and humidifies the air prior to delivery to the patient. A comfortable well-fitting mask will be provided to patients.

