5.7 Primary Endpoint Analysis

The primary endpoint measure is the change in the Energy and Vitality subscale of the SF-36 questionnaire from baseline (i.e., pre-treatment) to 3 months post-randomization. It is a continuous variable.

The primary endpoint will be analysed using a mixed-effects repeated measures model to account for missing values. The model will be set up as follows: The Energy and Vitality subscale is the dependent variable, visit (baseline and month 3) is the repeated measure (a fixed effect), subject and site are random effects (with subject nested in site) and treatment group by visit is a fixed effect. In the case that the primary endpoint was not homogeneous across study sites (as discussed in Section 5.3), a treatment by visit by site interaction will also be included in the primary endpoint model as a random effect. Results will be presented as the mean difference in the change score from baseline to 3 months (adjusted for baseline score, as appropriate) between the two treatment groups with a 95% confidence interval at 3 months and p-value for the treatment group effect.

As a sensitivity analysis of the primary endpoint, a similar mixed-effects repeated measures model to the above will be constructed, that also adjusts for other baseline and demographic variables that were found to be imbalanced between treatment groups per Section 5.6. The mean difference in change score from baseline to 3 months will be presented with a 95% confidence interval at 3 months.

For these analyses of the primary endpoint, a P-value of less than 0.05 will be used to indicate statistical significance. Analyses of the primary endpoint will be generated for the ITT-1 population.

A second sensitivity analysis for the primary endpoint will be generated using the CC-1 population.

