5.10 Additional Exploratory Analyses

Several of the exploratory analyses did not fit within the scope of the primary manuscript, and will be completed and reported at a later date:

- Summaries and analyses of secondary endpoints in patients with moderate OSA per AASM 2012 guidelines.
- Summaries and analyses of secondary endpoints comparing patients in the CPAP group who are adherent vs. not adherent to treatment.
- Summary of US Medicare definition of adherence.
- Predictors of adherence to CPAP therapy.
- Details of patient contacts.
- Summaries and analyses by gender.

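### The gender term planned in SAP 5.10 is a main effect on score level, so it does not address the objective of comparing change between arms by gender

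*SAP*

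**What the plan says.** SAP 4.5 lists as an exploratory aim: "Compare baseline symptoms and changes in quality of life scores from baseline to 3 months between Treatment and Control groups by gender". SAP 5.10 answers it in three steps. Baseline characteristics, AHI and quality of life scores are summarised by gender. Then, "Changes in quality of life scores from baseline to 3 months will be summarized descriptively by treatment group and gender". Last comes the only model step: "the effect of gender will be explored by including gender as a fixed effect in the analysis model described in Section 5.7".

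The model referred to is a mixed model for the score itself: "The Energy and Vitality subscale is the dependent variable, visit (baseline and month 3) is the repeated measure (a fixed effect"). Its random part consists of site and of patient within site. The treatment term is worded thus: "treatment group by visit is a fixed effect". No gender-by-visit or treatment-by-visit-by-gender term is named anywhere.

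The Protocol sets the CPAP mode by sex. Section 9.2 states that "male patients will be given the AutoSet using Response Setting and female patients will be given the AutoSet for Her", and section 5.5.1 gives the same rule. The SAP's gender text does not mention this.

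The amendment in SAP 8 keeps the primary model. It moves sensitivity and secondary analyses to a baseline-adjusted ANCOVA with last observation carried forward, and it puts "Summaries and analyses by gender" among the items to be reported later.

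**The concern.** The aim concerns change from baseline, compared between arms, by gender. The one model term offered concerns the average level of the score in men and women. For age, BMI and AHI, SAP 5.10 speaks explicitly of variation in treatment effect; for gender, the named term does not measure that.

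A reader of the later report would see a p-value for gender beside a table of changes by arm and gender, and would naturally connect the two. The p-value could be small only because women and men start at different vitality levels. It could be large although CPAP works differently in the two sexes.

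Interpretation is a separate matter. In the CPAP arm sex and device mode go together one to one, so even a correctly fitted interaction needs a stated limit on what it can be attributed to.

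**Working it through.** **1. The plan's own figure.** Inputs from SAP 4.6 and Protocol 11.2.1: mean changes 10.8 and 4.2 (difference 6.6), SDs 17.0 and 18.1, two-sided 5%, 80% power.
- Pooled SD = √((17.0² + 18.1²)/2) = √308.3 = 17.56.
- n per arm = 2 × (1.960 + 0.842)² × 308.3 / 6.6² = 111.1, so 112 per arm and 224 in total. This reproduces the plan. No figure is given for the gender analysis.

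**2. What the planned term does.** Let t be arm, v visit (0 or 1) and g gender (1 = woman). The planned mean is

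α + βv + γt + δtv + λg.

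Month 3 minus baseline is β + δt, so λ has cancelled. The arm difference in change is δ for both sexes by construction.

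In one simulated complete data set of 224, adding gender left the treatment-by-visit estimate at 5.8901 (SE 2.345), unchanged. With 10% of month-3 scores missing, the shift over 150 runs averaged −0.002 points and was at most 0.32. These fits used a random subject effect only. A site intercept also cancels from the change.

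**3. What λ picks up.** Suppose women differ from men by G at baseline, by a further C in change common to both arms, and by D in CPAP effect. With complete data and equal allocation within each sex, λ is the sex difference in the two-visit mean, averaged over arms:

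λ = G + C/2 + D/4.

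D is present at one of two visits and in one of two arms, hence the quarter. With G = 5, C = 0, D = 13.2 this gives 5 + 3.3 = 8.3; the 150 runs averaged 8.5. In the same runs, the model with the three-way term averaged 14.0 for D (run-to-run SD 4.75, so simulation SE 4.75/√150 = 0.4).

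**4. How it can mislead (illustration).** None of these inputs is in the documents: half women, C = 0, between-subject SD 14, residual SD 12.4 per visit (change SD 12.4 × √2 = 17.54), and the values of G and D.
- SD of the two-visit mean = √(14² + 12.4²/2) = 16.52, so SE(λ) = 16.52 × √(4/224) = 2.21.
- SE(interaction) = 17.54 × √(4/56) = 4.69.
- Chance of p < 0.05 ≈ Φ(|estimate|/SE − 1.96), or 5% when the true value is zero.

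| D | G | Expected λ | λ significant | Interaction significant |
|---|---|---|---|---|
| 13.2 | 0 | 3.3 | 32% | 80% |
| 13.2 | −3.3 | 0.0 | 5% | 80% |
| 0 | −6 | −6.0 | 78% | 5% |

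Simulations of 2,000 trials per row gave 32–34%, 4–5% and 76–77% for λ, and 80–81%, 80–81% and 4–5% for the interaction. The −3.3 was chosen to offset D/4 exactly.

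**5. Precision of the right term.** SE = 17.56 × √(2/w + 2/m), with w women and m men per arm and w + m = 112. The female share is assumed.

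| Female share | SE | 95% CI half-width | Detectable at 80% | Power for 6.6 |
|---|---|---|---|---|
| 50% | 4.7 | 9.2 | 13.1 | 29% |
| 40% | 4.8 | 9.4 | 13.4 | 28% |
| 30% | 5.1 | 10.0 | 14.3 | 25% |
| 20% | 5.9 | 11.5 | 16.4 | 20% |

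If 10% of the 224 have no month-3 score, each SE rises by about 1/√0.9 = 1.05. Points are on the scale of the planning SDs.

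**6. Device mode.** All men on CPAP have one mode, all women on CPAP the other, and controls have none. The interaction is therefore the effect of CPAP in the women's mode among women minus the effect of CPAP in the men's mode among men. No patient of either sex uses the other mode, so no model can split this contrast into sex and mode.

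**The case against.** The strongest reply is that the aim in SAP 4.5 asks for a comparison by gender and names no interaction test, and that the descriptive outputs provide one. This largely stands. The baseline summary and the table of changes by arm and gender cover both halves of the aim, and the table yields each sex's CPAP-minus-control difference as a point estimate. A reader might infer that the gender aim cannot be answered as planned; the documents do not support that. What the plan lacks is a stated arm difference, a confidence interval and an interaction.

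Gender is also a minimisation factor (SAP 4.7), so including it as a covariate is legitimate. That justifies the term as an adjustment, not as a way to explore the effect of gender on change.

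The amended ANCOVA changes the algebra. There a gender term relates to the month-3 score given baseline and does not cancel. But SAP 5.10 points to the 5.7 model, which was kept for the primary endpoint, and a gender main effect in an ANCOVA is still not a treatment-by-gender term.

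Finally, SAP 1 leaves later exploratory work unbound by the plan, so an interaction can already be added. That is true and limits the weight of the point. It does not make the term that is written down the right one.

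**Conclusion.** The point holds for the model term. As written, the coefficient is an average level difference that cancels from the change. It carries a quarter of any sex difference in CPAP effect, mixed with any baseline gap. It would be too strong to say that it holds no trace of the interaction; the trouble is that the trace cannot be separated out.

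The cancellation is algebra and needs no assumption about the data. The exact quarter needs complete data and equal allocation within each sex. The error rates in the illustration depend on inputs absent from the documents and show direction, not expected size.

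A reader might also infer that assigning mode by sex invalidates the gender comparison. It does not: CPAP against control within each sex remains a valid randomised comparison of CPAP as delivered. It only prevents attributing a difference between the sexes to sex itself, and neither document claims to do so.

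The correct term will be imprecise: the difference detectable with 80% power is 13.1 to 16.4 points, about twice the planned effect of 6.6 or more. Because the analysis is exploratory, tests no primary or secondary hypothesis and is deferred, this is a minor-to-moderate correction.

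**What to change.** In SAP 5.10, replace the gender main effect with gender, gender-by-visit and treatment-by-visit-by-gender terms in the 5.7 model. For endpoints analysed by the amended ANCOVA, add gender and treatment-by-gender. Report the Treatment minus Control difference in change for men and for women, and the interaction, each with a 95% CI. Make no claim from a gender main effect.

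Add two statements. First, the interaction has low precision, so a non-significant result is not evidence of equal effects. Second, CPAP mode is determined by sex, so a sex difference is that of CPAP as delivered and will not be attributed to sex alone. No change to device settings is implied.

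The cost is a few lines of SAP text and one changed model statement, with no new data. Since the gender analyses are still to be reported, the wording can be settled beforehand. The drawback is a wide interval that may leave the question open.
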